We propose a single center, placebo-controlled, randomized double blinded 90 (+/- 5) day trial, to study the effect of IC-CBAS delivery (500 mg BID for the first week and 1000 mg BID for the rest of the study) on colonic EEC function, postprandial incretins (GLP-1, PYY₃₋₃₆, FGF-19, and OXM), body weight, and satiety (evaluated with gastric emptying and appetite based VAS) in patients with obesity and abnormal satiety. We plan to randomize 18 participants per group. Participants will complete the following visits: 1) Screening and Consent (virtual); 2) Baseline phenotype, lifestyle intervention, 3) Colonoscopy and Randomization visit prior to medication start (in first 6 patients in each arm) who are willing to consent to colonoscopy), 4) Two (in person or virtual) Study Team visits at 30 & 60 days post randomization, 5) Colonoscopy visit and 6) Exit Phenotype visit after taking last medication dose (in first 6 patients in each arm). During the phenotype visits, participants will be phenotyped by measuring energy expenditure, satiety with gastric emptying of solids and VAS scores, satiation with calories consumed to fullness, and emotional eating by questionnaires[8]. Resting energy expenditure will be measured by indirect calorimetry, gastric emptying will be assessed with scintigraphy and calories to fullness will be tested in *ad libitum* meal. In addition, participants will have a body composition with a DEXA scan. Blood will be collected every 30 minutes for 6 hours and selected plasma gastrointestinal hormones will be measured. A sample will be stored for venous blood DNA analysis. Stool samples will be collected for 24 hours for microbiome, bile acids and short chain fatty acids. Participants will keep a food, medication, and activity diary. Participants

will receive a bowel prep (Movi-prep) and follow standard colonoscopy preparation guides. The next day, after an overnight fasting, a colonoscopy with terminal ileum intubation will be performed. The colonoscopy will be done in the GI clinical or research unit and will be supported by sedation based on patients' characteristics (i.e., conscious sedation vs. anesthesia supported sedation). During the procedure, 8 biopsies will be obtained from the ilium, right and left colon. During the Study Team visits, patients will meet with the study team to review medication compliance, assess adverse events, and perform a medication dispensation.

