- Participants will meet with the study team (either in person at the CRTU or virtually) approximately 30 days after visit 2. The study team will assess adverse events, medication compliance, and perform a new medication dispensation (if visit is virtual the medication will be shipped to the participant's preferred address).

- **Visit 4: Study Team visit**

Participants will meet with the study team (either in person at the CRTU or virtually) approximately 30 days after visit 3. The study team will assess adverse events, medication compliance, and perform a new medication dispensation (if visit is virtual the medication will be shipped to the participant's preferred address).

- **Visit 5: Colonoscopy #2**

- Visit 5 will only be completed in the first 6 patients of each group who are willing to consent to both colonoscopy visits.
 - Participants will receive a bowel prep (Movi-prep) during visit 5 and follow standard colonoscopy preparation guides. The next day, after an overnight fasting, a colonoscopy with terminal ileum intubation will be performed. The colonoscopy will be done in the GI clinical or research unit and will be supported by sedation based on patients' characteristics (i.e., conscious sedation vs. anesthesia supported sedation). During the procedure, 8 biopsies will be obtained from the ilium, right and left colon.

- **Visit 6 – Exit Phenotyping**

- Visit 6 will occur within 7 days of Visit 3. Phenotyping will be performed as at the baseline phenotyping visit including the questionnaires performed in screening visit.

Primary Endpoint:

The primary endpoint is EEC function measured through satiety hormones' (GLP-1 & PYY AUC and absolute plasma value curves) comparison between intervention and placebo groups at day 90 in APS-OB phenotype participants.

Secondary Endpoint:

Evaluation of obesity phenotypes through gastric emptying T_{1/2} for solids, satiety sensation with a visual analogue scale (VAS), fullness (VAS), hunger (VAS), desire to eat (VAS), appetite overall score (VAS), ad-libitum buffet meal food intake (kcal), microbial changes, behavioral questionnaires, energy expenditure, and body weight in APS-OB phenotype participants intervened with IC-CBAS, compared to placebo.

Statistical Analysis:

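### The Visit 6 timing rule contradicts the day-90 exit test, and the visit order puts the exit bowel prep before the GLP-1/PYY measurement in up to 12 participants

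*Combined protocol and SAP*

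**What the plan says.** Under Visit 6 – Exit Phenotyping, the timing rule is "Visit 6 will occur within 7 days of Visit 3", and the content is fixed by "Phenotyping will be performed as at the baseline phenotyping visit". Visit 3 is set "approximately 30 days after visit 2", and the Design section places the two study-team visits at 30 and 60 "days post randomization". The Methods section schedules the repeat phenotyping at day 90 (+/- 5) for subjects generally. The Primary Endpoint section specifies a "comparison between intervention and placebo groups at day 90".

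The second colonoscopy applies to a subset: "Visit 5 will only be completed in the first 6 patients of each group". Its preparation is described as "Participants will receive a bowel prep (Movi-prep) during visit 5", with the procedure the following day. The Design section lists the closing visits as "5) Colonoscopy visit and 6) Exit Phenotype visit after taking last medication dose". At baseline the order is the other way round: phenotyping is Visit 1 and the colonoscopy follows at Visit 2, 3 to 5 days later.

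On dosing, the synopsis places the second colonoscopy after the final dose, while Methods gives a dose 30 minutes before the exit test meal. On stool, the baseline specimen is timed 48 hours before Visit 1, but the exit specimen is described only as collected after treatment.

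**The concern.** Visit 6 produces the primary endpoint, so its timing rule should be right and should apply to every participant. As written it cannot be followed together with the day-90 requirement, and the obvious one-digit correction covers only the colonoscopy subset.

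The order of visits adds a second problem. The study drug is meant to act on cells of the ileum and colon, and the protocol assigns colonic bacteria a role in processing bile acids that are not reabsorbed. A bowel prep shortly before the exit test clears that site in up to a third of each arm and not in the rest. If this matters, the hormone curves, fecal bile acids and microbiome become more variable for a reason unrelated to treatment. The Statistical Analysis section has no term or sensitivity analysis for colonoscopy status.

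**Working it through.** **1. The window as written.** Days are counted from randomization, because Visit 2 is itself described as taking place only in the colonoscopy subset.
- Visit 3 is at about day 30, so the rule gives 30 − 7 = 23 to 30 + 7 = 37.
- The exit visit in Methods is 90 − 5 = 85 to 90 + 5 = 95.
- The gap is 85 − 37 = 48 days, and the rule falls before Visit 4 (about day 60). Visit 3 would have to be on day 85 − 7 = 78 or later for the windows to touch.

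**2. Reading Visit 3 as Visit 5.**
- Participants with no Visit 5: 36 − 12 = 24.
- For the other 12, with the 7 days counted from the colonoscopy, the test falls 0 to 7 days after it. The prep was the day before, so it falls 1 to 8 days before the test. No minimum is set.

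**3. Order.**

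| | First | Second |
|---|---|---|
| Baseline | Phenotyping (Visit 1) | Prep and colonoscopy (Visit 2) |
| Exit | Prep and colonoscopy (Visit 5) | Phenotyping (Visit 6) |

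**4. Dosing.** If the dose before the exit meal is the last one, the synopsis puts the colonoscopy after the exit test, against the visit numbering. If the colonoscopy comes first, it is not after the last dose. The two statements fit only when phenotyping precedes colonoscopy.

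**5. Stool.** If the 48-hour timing carries over from baseline, a specimen taken 48 hours before Visit 6 falls after the prep whenever the prep was 3 or more days before Visit 6. In step 2 that covers most of the allowed range.

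**6. Share affected.**
- With no dropout: 6/18 = 33% of each arm.
- Upper bound: 6/12 = 50%, if each arm falls to the 12 that the plan powers on and all 6 colonoscopy participants remain. Dropout spread evenly leaves it at 33%.

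**7. Scale, by assumption only.** The plan's inputs are a GLP-1 AUC difference of 3223 and an SD of 3125.
- Plan's figure: n = 2(z_α + z_0.80)²(SD/difference)². With one-sided alpha 0.05 this is 2 × (1.645 + 0.842)² × (3125/3223)² = 11.6, so 12 per group. Then 12/0.7 = 17.1, so 18 per group and 36 in total. Two-sided alpha 0.05 gives 15 by the same formula, or 16 with the t distribution. That is a separate matter. The power figures below use a two-sided 0.05 t-test.
- Common shift of k SDs in the subset of both arms: SD becomes 3125 × √(1 + k²f(1 − f)), where f is the share affected.

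| k | SD at f = 1/3 | Power, 18 per arm |
|---|---|---|
| 0 | 3125 | 85.2% |
| 0.25 | 3147 | 84.7% |
| 0.5 | 3211 | 83.3% |
| 1.0 | 3455 | 77.6% |

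At 12 per arm with 6 affected, power goes from 67.5% to between 66.9% (k = 0.25) and 57.9% (k = 1.0).
- Loss of drug effect in the subset: the arm difference falls by f × fraction lost × 3223. A 10% loss gives 1/3 × 0.10 × 3223 = 107 (3.3%), or 0.50 × 0.10 × 3223 = 161 (5.0%) at the upper-bound share. A 50% loss at 18 per arm leaves 3223 × (1 − 1/6) = 2686, with power 70.7%.

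None of the values of k or of effect lost comes from the documents.

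**The case against.** The strongest reply is that the anchor is an editorial slip which the protocol already resolves. Methods gives a day-90 exit visit without limiting it to the colonoscopy subset, and the endpoint and analysis sections agree. This largely stands. A reader might infer that the primary test would be run near day 30, or that 24 participants have no scheduled exit day, and the documents do not support either. What remains is a wrong instruction in the visit schedule itself, and Methods says nothing about the interval between prep and test.

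No section says that bowel prep alters later GLP-1 or PYY responses, and the order rests on visit numbering and the Design list, with the synopsis pointing the other way. Both points stand, so the harm is a plausible risk of unknown size. It is also tempting to read a dosing interruption into the conflict between synopsis and Methods. The documents prescribe none: dosing runs for 90 (+/- 5) days and includes a dose before the exit meal. The conflict shows only that the last dose is not clearly placed.

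The primary comparison is between arms at day 90, with no stated baseline hormone adjustment. The reversed order therefore does not distort a change score in the primary analysis. That stands too. The relevant contrast is between participants prepped just before the exit test and those not prepped. Finally, biopsies serve the aim of studying enteroendocrine function, so moving them later is a real trade-off that calls for a short interval.

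**Conclusion.** The concern holds as a scheduling contradiction and an avoidable source of noise, and should be corrected. The written window misses the earliest permitted exit day by 48 days. Substituting Visit 5 is not a complete repair. Up to 12 participants, 33% of each arm without dropout and at most 50% on an extreme dropout pattern, may have the exit hormone test, and possibly the exit stool sample, soon after a bowel prep.

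The effect on the hormone, fecal bile-acid and microbiome results cannot be derived from the documents and may be zero. A moderate shift common to both arms would cost little power: 85.2% to 83.3% for an assumed 0.5 SD at 18 per arm. A reader might infer a biased treatment comparison. The documents do not show that, because both arms follow the same order with the same planned number of colonoscopies. Bias would need the prep to interact with the drug or the subset to become unbalanced.

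**What to change.** Replace the Visit 6 rule with day 90 (+/- 5) after randomization for all 36 participants. In the colonoscopy subset:
- collect exit stool and complete exit phenotyping before the exit prep;
- continue dosing without interruption through the dose before the exit test meal, and name that as the last dose;
- start the prep after the exit test and do the colonoscopy the next day, or as soon as feasible, so that biopsies are taken close to the last dose. The 3 to 5 days used at baseline would be too long here.

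This mirrors the baseline order and reconciles the synopsis with Methods. The cost is protocol wording and a swap of two visits for at most 12 people, with no added procedure. The downside is that biopsies come about a day after the last dose, which is consistent with the synopsis.

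If the present order is kept, correct the anchor, state that dosing continues through Visit 6, set a minimum interval between prep and exit test, and collect exit stool before the prep.

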We believe these effects can be seen after metabolic surgery, where bile acid secretion increases significantly after Roux-in-Y gastric bypass surgery. Recent studies showed colonocytes express BA signaling machinery and deficiency of said machinery in patients with obesity and diabetes. In humans, the acute infusion of taurocholic bile acid enemas per rectum or via nasojejunal feeding resulted in rapid increase in GI satiety hormones and increased satiety [24, 25]. Bile acids need to be delivered to the distal ileum and colon to stimulate only distal L-cells and avoid proximal lipid absorption. Thus, it is critical to know, whether the delivery of IC-CBAS will restore the normal satiety in patients with ASP-OB. We hypothesize that the IC-CBAS delivery will stimulate EEC secretion in the distal jejunum, ileum, and colon, thereby increasing the secretion of GLP-1 and PYY₃₋₃₆. This will possibly restore satiety and induce weight loss in APS-OB phenotype subjects.

The overall research goal is to study the effect of delayed-release IC-CBAS on satiety and body weight in APS-OB phenotype patients when comparing it to placebo. The current proposal is a proof of concept, single center, placebo-controlled, randomized clinical trial in otherwise healthy patients with obesity and abnormal satiety.

Preliminary Data:

Chenodeoxycholic acid delayed release: Initially, we completed a feasibility, 4-day, placebo control trial to test the effect of ileo-colonic delivery chenodeoxycholic (IC-CDCA) bile acid 500 and 1000 mg PO daily in 20 per group healthy volunteers. IC-CDCA produces weight loss in healthy subjects (fig 1). Posteriorly, we completed a 28 day, randomized, double-blinded, placebo-control trial to study the effect of IC-CDCA acid in glycemia in patients with obesity and type 2 diabetes[1].

Hypothesis:

IC-CBAS will stimulate EEC secretion in the ileum and colon, increasing the secretion of GLP-1 and PYY₃₋₃₆, FGF-19, oxyntomodulin (OXM), and restore normal satiety in patients with APS-OB.

RESEARCH PLAN:

Design:

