Height, weight, blood pressure, heart and respiratory rates, waist and hip ratio, waist circumference, and temperature.
- Baseline and follow-up characteristics studies:
- Methods of metabolic studies:
 - o Body composition will be measured by DEXA (dual energy x-ray absorptiometry).
 - o Resting energy expenditure was assessed by indirect calorimetry with a ventilated hood (Parvo Medics, Sandy, UT).

- Gastric emptying (GE) of solids by scintigraphy [9] [8, 11] Images will be acquired at 0, 30, 60, 90, 120 and 240 minutes following the normal clinical gastric emptying testing protocol without a push meal.
- Satiation will be measured by *ad-libitum* meal to measure total caloric intake and macronutrient distribution in the chosen food. Satiation will be reported in calories consumed at fullness (satiation) [8] [11].
- Appetite sensations by visual analog score fasting and every 30 minutes after the standard meal for GE and the Satiation test up to 2 hours [8, 11].
- Blood samples: The fasting blood samples will be collected during the gastric emptying meal and stored at -70° C freezer. We will analyze plasma glucose, insulin, C-peptide, GLP-1, PYY₃₋₃₆, OXM, FGF-19, 7- α -C4, Adiponectin, Leptin, CCK, Pancreatic Polypeptide (PP), serum bile acids, short chain fatty acids, amino acids[2, 8]. Samples collection, handling, and storage: Samples will be collected after an overnight fast (of at least 8 hours) in the morning. Plasma will be preserved following standard guidelines and protein degradation inhibitors, kallikrein and DPP-IV inhibitors will be added to preserve the samples. Samples will be stored at -80°C in the PI's laboratory. Plasma hormones and proteomics by radioimmunoassay and/or mass spectrometry measured fasting, postprandial, and every 30 minutes for 6 hours. The primary endpoint being the peak postprandial level (test should be done simultaneously to GE).
- Blood DNA for genome wide association studies (GWAS). These samples will be stored for future research.
- Stool samples: One random stool will be collected at baseline and after treatment for fecal bile acids, short chains fatty acids and microbiome.
- Participants with childbearing potential will undergo a pregnancy test.
- Self-administered questionnaires assessing affect, physical activity levels, attitudes, body image, diet, and eating behavior; details of each questionnaire are provided below.

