The primary analysis will compare AUC values between treatment and placebo groups after 90 days of IC-CBAS. Based on the previous study by Calderon et al.[1], we calculated a sample size of 36 subjects. They reported GLP-1 AUC significant difference between intervention and placebo group of 3223 mg/dl. We aim to detect a mean difference in AUC of 3223mg/dl and utilized their IQR to calculate a standard deviation of 3125mg/dl. To have 80% power to detect a difference of 3223mg/dl with a two-sample t-test would require 12 subjects per group. In order to allow for up to 30% dropout, we will enroll 36 subjects total. The effect on weight loss will be evaluated using analysis of covariance (ANCOVA) models, with relative weight loss as the dependent variable, adjusting for gastric emptying (T_{1/2}, min) and gender. Any power lost on degrees of freedom spent on covariate parameter estimation should be more than reclaimed by reduced error variation. For the rest of the endpoints we will compare the data on gastric emptying, satiation parameters, appetite scores, body composition, energy expenditure, GI hormones, bile acids and microbiota between intervention vs. placebo, using the same ANCOVA model. Transformations will be employed as needed for heavily skewed distributions. All treatment effect estimates will be reported with 95% confidence intervals.

POTENTIAL PITFALLS AND PRECAUTIONS TAKEN:

Potential pitfalls of minor significance in this study are:

- **Selection bias** - Participants willing to participate will likely be more motivated to lose weight than the general population. Randomization, double blind will avoid any selection bias;
- **Potential for type II error** - The sample sizes have been based on appropriate statistical power with allowance for drop out. Estimates of variation have been thoroughly characterized in the prior literature from our lab; and other internal and external studies for weight loss at 12 weeks.
- **Feasibility** - We have identified a cohort of people in our community who have obesity, abnormal satiety phenotype, and are willing to participate. We have the experience to successfully recruit 36 participants for the study.

Human Studies Aspects

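### The primary endpoint covers both GLP-1 and PYY with no rule for success, the test is unsettled, and one stray sentence calls the peak level primary

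*Combined protocol and SAP*

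**What the plan says.** - **Primary Endpoint section.** Enteroendocrine cell function is assessed through "GLP-1 & PYY AUC and absolute plasma value curves) comparison between intervention and placebo groups at day 90". That is two hormones, each with an AUC and a curve.
- **Statistical Analysis section, primary comparison.** "The primary analysis will compare AUC values between treatment and placebo groups after 90 days of IC-CBAS". No hormone is named.
- **Statistical Analysis section, sample size.** "They reported GLP-1 AUC significant difference between intervention and placebo group of 3223 mg/dl". With an SD of 3125 (units as printed), "To have 80% power to detect a difference of 3223mg/dl with a two-sample t-test would require 12 subjects per group". Only GLP-1 AUC is sized, and no alpha is given here.
- **Statistical Analysis section, other endpoints.** GI hormones are listed among the remaining endpoints, to be analysed with the ANCOVA used for weight loss, adjusted for gastric emptying half-time and gender.
- **Visit 1, blood-sample bullet.** Hormones are "measured fasting, postprandial, and every 30 minutes for 6 hours", and then: "The primary endpoint being the peak postprandial level (test should be done simultaneously to GE".
- **Study design summary.** The only stated alpha, 0.05, belongs to a different calculation, which sizes the same 36 participants on a 1 kg weight difference.
- **Reporting.** "All treatment effect estimates will be reported with 95% confidence intervals", which points to two-sided 5% without saying so.

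No section says whether AUC is total or incremental, or over what time window it is taken.

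**The concern.** With two hormones in the primary endpoint, three results could be called success: GLP-1 alone, PYY alone, or both. The plan does not choose. Accepting either hormone at 5% raises the false-positive rate. Requiring both leaves that rate controlled, but the power statement, made for GLP-1 AUC alone, no longer describes the trial. The undefined AUC and the two candidate methods leave further room for choice once the data are in. The peak sentence adds a direct textual conflict, because peak and AUC summarise the same curve differently and can disagree.

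**Working it through.** **Inputs from the documents.** Difference 3223 and SD 3125 for GLP-1 AUC; two-sample t-test; 12 completers per group; 18 enrolled per group; 1:1 allocation; 30% dropout.

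**Assumed, because the documents do not give it.** Two-sided 5% per test; unadjusted t-tests; correlation between the two AUCs of 0 to 0.9; PYY standardised effect of 0.5, 1 or 1.5 times GLP-1's. High correlations are included because the Background ties both hormones to one mechanism: "We hypothesize that the IC-CBAS delivery will stimulate EEC secretion in the distal jejunum, ileum, and colon, thereby increasing the secretion of GLP-1 and" PYY.

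**1. The plan's own figure.** d = 3223/3125 = 1.031. The exact t-test needs 15.78, so 16 per group, for 80% power at two-sided 5%. At one-sided 5% it needs 12.36, so 13 (12 by the normal approximation). With 12 per group, power for GLP-1 alone is 67.5% two-sided and 78.9% one-sided; with 18 it is 85.2% two-sided. The dropout step reproduces: 12/0.70 = 17.1, so 18 per group and 36 in total. The gap between 80% and 67.5% is a separate matter and is not counted against the missing rule.

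**2. Either AUC suffices.** At correlation 0 the false-positive rate is 1 − 0.95² = 9.75%. Simulated over correlation 0 to 0.9, it is 9.8% down to 7.1% at 12 per group and 9.7% down to 7.0% at 18. Counting benefit only, it is 5.0% down to 3.6%, against 2.5%. Power with equal effects at 12 per group is 1 − (1 − 0.675)² = 89.4% at correlation 0, falling to about 74% at 0.9.

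**3. Both AUCs required.** At correlation 0, power is the product of the two single-test powers; higher correlation raises it towards the smaller of the two. At 12 per group, the exact t-test gives PYY power of 22.7% for d = 0.516 (half) and 95.1% for d = 1.547 (1.5 times).

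| PYY effect relative to GLP-1 | Per group | Power at correlation 0 | Power over correlation 0 to 0.9 |
|---|---|---|---|
| 0.5 | 12 | 0.675 × 0.227 = 0.153 | 15-23% |
| 1 | 12 | 0.675 × 0.675 = 0.456 | 46-61% |
| 1.5 | 12 | 0.675 × 0.951 = 0.642 | 64-68% |
| 1 | 18 | 0.852 × 0.852 = 0.726 | 73-81% |

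**4. Cost of requiring both, without the sizing shortfall.** Taking 80% per hormone at face value (d = 1.197 at 12 per group), power for both is 0.80² = 64% at correlation 0 and about 75% at 0.9. Requiring both therefore costs 80 − 75 = 5 to 80 − 64 = 16 points.

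**The case against.** The best defence is that the plan is nearly unambiguous. Both headed sections agree on AUC, and the peak sentence sits in an assay bullet for the baseline visit, where it may be a leftover or mean only that assay's main summary. GLP-1 AUC is the only powered hormone measure. If the other GI hormones are what the ANCOVA sentence covers, GLP-1 AUC is the implied single primary, tested by t-test. This is also a 36-person proof-of-concept trial, where strict error control matters less.

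Much of this stands. A reader might infer that peak and AUC compete equally for primary status; the documents do not support that, since the primary analysis is committed to AUC. What remains is that the peak sentence still uses the words for the primary endpoint. A sizing assumption is also not a success rule, and the Primary Endpoint section lists PYY beside GLP-1 without ranking them. The ANCOVA sentence can equally be read as covering both AUCs, which makes the method itself uncertain.

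A reader might also infer that the trial has a false-positive rate near 10%. The plan never says that either hormone suffices, so this describes one permitted reading only. Nor does the missing rule itself cost power: requiring both lowers it, while accepting either raises it. Finally, if ANCOVA is used, the power figures here are only indicative, because the plan expects the covariates to more than repay the degrees of freedom they use.

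**Conclusion.** The point holds and should be fixed. The live ambiguity is which hormone or hormones decide the trial, which AUC is meant and which test is used; the peak sentence is a smaller inconsistency to reconcile. The two readings of success differ materially: a 7-10% false-positive rate if either suffices, against no inflation but 46-61% power at 12 per group if both are required with equal effects. The 12-per-group figures are the full-dropout case; with all 18 retained, both-required power is 73-81%. The false-positive range rests on the assumed correlation and unadjusted 5% tests. The power range rests even more on the PYY effect, for which the documents give nothing: varying it from half to 1.5 times GLP-1's moves both-required power at 12 per group from 15% to 68%.

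**What to change.** Before unblinding:

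1. Name GLP-1 AUC at Day 90 as the single primary endpoint, at two-sided 5%, in both the Primary Endpoint and Statistical Analysis sections.
2. State total or incremental AUC and its time window, matching the AUC behind the 3223 and 3125 figures.
3. Name one primary test, either the t-test or the ANCOVA already described, and take this endpoint out of the list of remaining endpoints.
4. Test PYY AUC next, in fixed sequence at 5%. Label peaks and curves supportive.
5. Align the peak sentence under Visit 1 and the 1 kg weight-based sizing in the Study design summary with this choice.

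The cost is wording only, with no added participants or procedures. The downside is that PYY can be claimed only if GLP-1 succeeds. If the assumed GLP-1 effect is real, GLP-1 still fails 100 − 67.5 = 32.5% of the time at 12 per group and 100 − 85.2 = 14.8% at 18 (unadjusted t-test).

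If the sponsor wants PYY to rank equally, requiring both or splitting alpha is acceptable, provided its power is stated. An equal split (2.5% each) gives GLP-1 55.6% power at 12 per group and 77.0% at 18. Requiring both with equal effects needs about 19 to 21 completers per group for 80% power (correlation 0.8 down to 0), which at 30% dropout is 19/0.70 = 27.1, so 28, to 21/0.70 = 30 enrolled per group.
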